6.1.6. Interim Analyses and Data Monitoring

An interim assessment of the treatment allocation will be performed to ensure that there is a sufficient number of subjects within and across treatment arms. A subject's MITT status (specifically positive fungal culture at baseline) is determined only after randomization which may result in an imbalance between treatment groups. Therefore, at least one assessment during the conduct of the study is planned to ensure that there is a sufficient number of subjects within each group for the primary analysis. Once at least 10 MITT subjects have been enrolled in the 7-Day active group, the numbers of MITT subjects in the 14-Day active group and the 14-Day

vehicle group will be determined by an unblinded statistician; no persons involved in the day to day conduct of the study will be unblinded. Randomization allocation for future subjects may be adjusted if deemed necessary to achieve minimum number of subjects within each arm. At the time of the assessment, the 7-Day active kits will be removed from the randomization schedule for future subjects and the table below will be used as a guide for adjustments to the randomization allocation of 14-Day kits for future subjects. This assessment may be repeated in order to ascertain that a minimum enrollment of MITT subjects is met for each treatment group before study end.

14-Day Active	14-Day Vehicle	Action
$\geq e + 3$	$\leq e - 3$	Skip 14-Day Active kits
$\geq e + 2$	$e - 2$	Skip 14-Day Active kits with the exception of one kit at each site. One of the four lowest 14-Day Active kit numbers will be selected at random to remain in the schedule for each site.
$e - 1$ to $e + 2$	$e - 1$ to $e + 2$	No action
$e - 2$	$\geq e + 2$	Skip 14-Day Vehicle kits with the exception of one kit at each site. One of the four lowest 14-Day Active kit numbers will be selected at random to remain in the schedule for each site.
$\leq e - 3$	$\geq e + 3$	Skip 14-Day Vehicle kits

Note: e represents the expected number of subjects based on a 1:1 ratio and the current number of MITT subjects between the 14-Day active and 14-Day vehicle groups. $e = \frac{1}{2} * (\text{Current number of MITT subjects between the 14-Day groups})$, non-integer results will be rounded down to the nearest integer. When determining an action the conditions of both the 14-Day Active and 14-Day Vehicle columns must be met.

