## **10.2 Hypotheses**

No formal hypotheses will be tested in this study. Descriptive comparisons will be made between the miconazole oil and the oil vehicle groups for subjects randomized to the 14-day groups. Additionally, descriptive comparisons will be made between the 7-day and 14-day groups for subjects randomized to the miconazole oil treatment.

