### **10.5.5 Interim Treatment Allocation Assessment(s)**

A subject's MITT status (specifically positive fungal culture at baseline) is determined only following randomization, which may result in imbalance between treatment groups. Therefore, at least one assessment during the conduct of the study is planned to ensure that there is a sufficient number of subjects within each group for the primary analysis. Once at least 10 MITT subjects have been enrolled in the 7-Day active group, the numbers of MITT subjects in the 14-Day active group and the 14-Day vehicle group will be determined by an unblinded statistician; no persons involved in the day to day conduct of the study will be unblinded. Randomization allocation for future subjects may be adjusted if deemed necessary to achieve minimum number of subjects within each arm.

Full details will be provided in the SAP.

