4.1.2. Method of Assigning Subjects to Treatment Groups

A randomization schedule will be generated in SAS® using PROC PLAN by a member in the QST Consultations, Ltd. (QST) Statistical Services department who is not associated with the conduct or analysis of the study. The randomization schedule will be stratified by site and separate lists will be produced for each site. Sites will receive sequentially numbered kits randomized in blocks of six in a 1:1:1 ratio.

At the Baseline/Day 1 visit, qualified subjects will be assigned to the lowest numerically available kit at the time of randomization. The assignment of the lowest numerically available kit number must be strictly adhered to as it is the method of randomization for this study. The kit number will be recorded in the electronic case report form (eCRF). Subjects will be randomized in a 1:1:1 ratio to one of three groups: 1) 7-day treatment with miconazole oil; 2) 14-day treatment with miconazole oil; or 3) 14-day treatment with miconazole oil vehicle.

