6. STATISTICAL AND ANALYTICAL PLANS

6.1. General Methodology

All statistical processing will be performed using SAS® unless otherwise stated. No interim analyses are planned.

No formal hypotheses will be tested in this study. Descriptive comparisons will be made between the micronazole oil and the oil vehicle groups for subjects randomized to the 14-day groups. Additionally, descriptive comparisons will be made between the 7-day and 14-day groups for subject's randomized to the miconazole oil treatment.

Descriptive statistics will be used to provide an overview of the efficacy and safety results. For categorical parameters, the number and percentage of subjects in each category will be presented. For continuous parameters, descriptive statistics will include n (number of subjects), mean, standard deviation (SD), median, minimum, and maximum.

The primary method of handling missing efficacy data will be the method of last observation carried forward (LOCF) imputation.

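### The 7-day arm closes at the first allocation assessment while 14-day enrolment continues, so the pooled 7-v-14 comparison can include 14-day subjects with no concurrent 7-day counterpart

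*SAP*

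**What the plan says.** **Allocation.** SAP 4.1.2 starts with lists stratified by site: "Sites will receive sequentially numbered kits randomized in blocks of six in a 1:1:1 ratio". SAP 6.1.6 sets the trigger for the assessment: "Once at least 10 MITT subjects have been enrolled in the 7-Day active group". At that point "the 7-Day active kits will be removed from the randomization schedule for future subjects". No condition is attached to this step. The action table that follows guides "adjustments to the randomization allocation of 14-Day kits for future subjects", so the 7-day arm closes even when the table's no-action row applies. The section adds: "This assessment may be repeated in order to ascertain that a minimum enrollment of MITT subjects is met". Protocol 4.4 also lets enrolment go beyond about 75 subjects.

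Protocol 10.5.5 is looser: "Randomization allocation for future subjects may be adjusted if deemed necessary to achieve minimum number of subjects within each arm". It does not mention closing the 7-day arm and leaves the details to the SAP.

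**Analysis.** Comparing 7 with 14 days is one of the two objectives (Protocol 2, SAP 3), and SAP 6.1 says "descriptive comparisons will be made between the 7-day and 14-day groups". The MITT population (SAP 6.4.2) is not limited by date of randomisation. SAP 6.7.1 and Table 14.2.1.1 give one cure percentage per arm. Covariates, centre and subgroups are each marked as not applicable (SAP 6.1.4, 6.1.7, 6.1.11). No concurrent-only set and no display before and after the assessment is planned.

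**The concern.** Randomisation protects the duration comparison only among subjects who could have been assigned either duration. Once the 7-day kits are gone, a new subject can receive only a 14-day kit. Pooling these later subjects with the earlier 14-day active subjects makes the 7-v-14 contrast partly a comparison with a different period. If cure rates, case mix or contributing sites change between periods, that change is read as an effect of duration, and the planned summary tables would not separate the two.

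The calendar span is not trivial. Amendment 4 (11 May 2018) already reports a lower than planned yield, so subjects had been enrolled by then. The allocation assessment entered with Amendment 5 (17 April 2019), eleven months later. Duration is also unmasked, so after closure sites know before enrolling that a subject will be treated for 14 days.

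**Working it through.** **The plan's own figure.** There is no power calculation to reproduce: Protocol 10.3 and SAP 7 say the sample size has no statistical basis. Protocol 3.1 plans about 75 subjects for about 10 evaluable in each of three arms, which implies an evaluable rate of 3 × 10 / 75 = 40%. That is derived from the 75 and does not confirm it. The documents state no culture-positive rate, so the MITT rate p is an assumption, shown from 30% to 83% (83% = 30/36, from the superseded planned number).

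**Step 1: how often is the 14-day active arm short when the 7-day arm closes?** Without blocking, the two arms race 1:1 to 10 MITT subjects. If K is the 14-day active count when the 7-day arm reaches 10, then P(K = k) = C(9+k, k) / 2^(10+k). This does not depend on p.
- P(K < 10) = 0.50, by symmetry.
- Mean top-up to 10 = 10 × C(20,10) / 2^20 = 10 × 184,756 / 1,048,576 = 1.76 subjects, or 17.6% of an arm of 10. When the arm is short, the mean shortfall is 1.76 / 0.50 = 3.5.
- P(share ≥ 30%) = P(K ≤ 7) = 0.31.

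Blocking lowers these a little. In a simulation with 10 sites, blocks of six, p of 40% and 50%, and 8,000 trials per rate, P(short) = 0.50. The mean shortfall when short is 3.1 and 2.9, the mean non-concurrent share 15.4% and 14.6%, and P(share ≥ 30%) 0.28 and 0.26.

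**Step 2: dependence on the stopping rule.** A second simulation (4,000 runs per scenario) applied the SAP 6.1.6 table. It assumed immediate culture results, read the fourth row as retaining one vehicle kit per site, and ended a skip once the two 14-day arms were level. Mean non-concurrent share of 14-day active MITT subjects:

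| Enrolment stops | p = 30% | 40% | 50% | 60% | 83% |
|---|---|---|---|---|---|
| At exactly 75 | 4% | 14% | 30% | 44% | 63% |
| When every arm has 10 MITT | 18% | 18% | 18% | 17% | 16% |
| At 75 or more and every arm at 10 | 18% | 20% | 30% | 44% | 63% |

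In the second row, at least one such subject occurs in about 57% of runs, and the 5th to 95th percentile of the share is 0 to about 60%. Stopping at exactly 75 with p = 40%, the assessment is reached in 57% of runs.

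**Step 3: effect on the contrast.** Shift in the 7-v-14 difference = non-concurrent share × change in cure rate between periods. The change is an assumption.
- 15% × 20 points = 3 points.
- 50% × 20 points = 10 points.

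**Step 4: sampling error.** At a cure rate of 50%, the 95% half-width is 1.96 × √(0.25/n1 + 0.25/n2).
- 10 v 10: 1.96 × √0.05 = ±44 points.
- 10 v 16 (pooled): 1.96 × √0.0406 = ±40 points.
- 10 v 7 (concurrent only, arm short by 3): 1.96 × √0.0607 = ±48 points.

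**Step 5: 14-day active v vehicle.** Closing the 7-day arm leaves both 14-day arms open. However, four of the five rows in the SAP 6.1.6 table skip one 14-day arm's kits, wholly or all but one per site. With 10 sites and p of 40-50%, a skip row applies at the first assessment in roughly 29-33% of simulated trials. While it applies, new subjects go wholly or mostly to one 14-day arm.

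**The case against.** The study is descriptive (Protocol 10.2: "No formal hypotheses will be tested in this study"), so no error rate is affected. With about 10 per arm, a shift of about 3 points is lost in ±44. The documents report no drift and no change in site mix. The top-up exists to reach a minimum number per arm, and a concurrent-only display removes it just when it was needed. In the second simulation the 14-day active arm has 9.6 to 9.8 concurrent MITT subjects on average, but the 5th percentile is about 4. All of this stands. It limits the weight of the point and argues for two displays rather than replacing one with the other.

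A reader might infer that the problem could never be seen. That goes too far. Listing 16.1.7 shows randomisation date and arm, and Listings 16.2.6.1 and 16.2.8.2.1 show signs, symptoms and cultures by subject, so a split could be made by hand. The gap is in the summary tables.

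A reader might also infer that 14-day active v vehicle is safe because both arms stay open. The skip rows of SAP 6.1.6 contradict this.

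**Conclusion.** The point holds as a cheap improvement, not as a flaw that invalidates the comparison. SAP 6.1.6 creates a period in which only 14-day kits are assigned, and SAP 6.7.1 pools across it for a stated objective. The share of about 15% rests on topping up the 14-day active arm only to 10 MITT subjects, an assumed culture-positive rate of 40-50% and 10 sites; under that rule about half of trials have no affected subject. Other stopping rules give mean shares from 4% to 63%, and the documents do not settle which rule applies.

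It would be tempting to conclude that the 7-v-14 result will be biased. The documents support only a risk of confounding with time: they show no drift, and the 20-point change used to size the shift is an assumption.

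**What to change.** In SAP 6.7.1, before unblinding:

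- Present the 7-v-14 comparison on MITT subjects randomised while 7-day kits were still in their site's schedule, alongside the all-subjects version. Define the flag from the randomisation date and the recorded date of kit removal at the site.
- Keep all subjects for 14-day active v vehicle. If a skip row is triggered, add a supportive display of that comparison before and after the allocation change.

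The cost is one flag, one or two extra tables, and a few fewer 14-day subjects in the concurrent duration display: about 2 on average if enrolment stops once every arm has 10 MITT, and about 2 to 8 if it runs to at least 75 at a 40-60% MITT rate. The site removal dates must be captured, because no planned listing shows them.

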### 9.2 Randomization

Subjects will be randomized in a 1:1:1 ratio to one of three groups: 1) 7-day treatment with miconazole oil; 2) 14-day treatment with miconazole oil; or 3) 14-day treatment with miconazole oil vehicle. Interim assessments are planned to ensure that there is a sufficient number of subjects within each group for the primary analysis. If deemed necessary the randomization ratio may be adjusted following the interim assessments; see [Section 10.5.5](#) for details.

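### Once the 7-day kits are withdrawn, rows 1 and 5 of the SAP's interim table leave a single 14-day product, so subjects enrolled after that change have no concurrent randomised comparator, yet are pooled by arm with earlier subjects

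*SAP*

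**What the plan says.** **Trigger.** SAP 6.1.6 sets the assessment by the 7-day arm: "Once at least 10 MITT subjects have been enrolled in the 7-Day active group", an unblinded statistician counts the MITT subjects in the two 14-day arms.

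**Closure of the 7-day arm.** "At the time of the assessment, the 7-Day active kits will be removed from the randomization schedule for future subjects".

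**Action table.** The two 14-day counts are compared with a reference value e: "e represents the expected number of subjects based on a 1:1 ratio", computed as half the current 14-day MITT total, rounded down.
- Row 1 (active at least e + 3, vehicle at most e - 3): "Skip 14-Day Active kits", with no exception.
- Row 2 (active at least e + 2, vehicle e - 2): "Skip 14-Day Active kits with the exception of one kit at each site", that kit being chosen at random from the four lowest active numbers.
- Row 3: no action.
- Row 4 (active e - 2, vehicle at least e + 2): vehicle kits are skipped except for one per site, but the sentence that selects the retained kit refers to active kit numbers.
- Row 5 (active at most e - 3, vehicle at least e + 3): "Skip 14-Day Vehicle kits", with no exception.

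The table is described as a guide. The assessment may be repeated.

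**Assignment.** SAP 4.1.2: "qualified subjects will be assigned to the lowest numerically available kit at the time of randomization". Kits come in site-specific blocks of six at 1:1:1.

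**Protocol.** Section 9.2: "If deemed necessary the randomization ratio may be adjusted following the interim assessments". Section 10.5.5 allows allocation of future subjects to be adjusted to reach a minimum number per arm and leaves the details to the SAP.

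**The concern.** The order of kits in the list is the trial's only source of randomness. When the list holds one product, the next subject's treatment is fixed.

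Subjects added in that period enter one arm only. They can differ from the opposite arm in enrolment time and in site mix. Nothing in the SAP would show or adjust for this: covariates (6.1.4), multicentre aspects (6.1.7) and subgroups (6.1.11) are all marked not applicable, and no display separates subjects enrolled before and after the change.

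The contrast affected is the first objective, 14-day miconazole oil against 14-day vehicle, with only about 10 evaluable subjects intended per arm (Protocol 3.1). In arms of that size a few non-concurrent subjects can move the cure percentage visibly.

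**Working it through.** The documents give no power, error rate or probability for this rule, so there is no figure to reproduce.

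**1. Products left.** Three products, minus the 7-day kits, minus one skipped 14-day product: 3 - 1 - 1 = 1. Under row 1 or row 5 the chance that a later subject receives the remaining product is 100%.

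**2. What triggers rows 1 and 5.** Let A and V be the 14-day active and vehicle MITT counts, with e = floor((A + V)/2). With an even total, a gap of 6 puts the arms at e + 3 and e - 3. With an odd total, a gap of 5 gives e + 3 and e - 2 (row 2 or 4), and a gap of 7 gives e + 4 and e - 3. Rows 1 and 5 therefore apply when the gap is 6 or more, rows 2 and 4 at a gap of 4 or 5, and row 3 at 3 or less. Coded and run over all 1,600 pairs of counts from 0 to 39, each pair meets exactly one row.

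Examples with total 20, e = 10: 13 v 7 is row 1, 7 v 13 is row 5, 12 v 8 is row 2, 11 v 9 is row 3.

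**3. How likely.** Let p be the share of randomised subjects who enter the MITT population. The documents do not state it. Protocol 3.1 plans 75 subjects for about 10 evaluable in each of three arms, so 30/75 = 40% is implied; 50% and 60% are shown as a range. The trigger of 10 MITT subjects in the 7-day arm corresponds to about n = 10/p subjects randomised per arm. With A and V independent Binomial(n, p):

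| p | n = 10/p | P(row 1 or 5) | P(row 2 or 4) |
|---|---|---|---|
| 40% | 25 | 11.1% | 20% |
| 50% | 20 | 8.1% | 19% |
| 60% | 16.7, taken as 17 | 5.3% | 17% |

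A simulation of blocks of six by site, stopped at the tenth 7-day MITT subject (20,000 runs per setting, 1 or 10 sites), agrees. Rows 1 and 5 together occur in 11% to 12% of runs at 40% yield and 8% to 10% at 50%. The wider range is 14% at 30% yield to between 3% and 8% at 70%.

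**4. How many subjects.** In triggered runs the median shorter arm is 7. From 13 v 7 the shortfall against 10 is 10 - 7 = 3, which is 3/10 = 30% of that arm's target. At 40% yield this takes 3/0.40 = 7.5, about 8 enrolled subjects, all on one product.

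**5. Row 4.** Its first sentence implies that one vehicle kit stays at each site; its second selects the retained kit from active numbers. No vehicle kit is therefore identified to stay. Applied literally, row 4 leaves only active, as row 5 does. By symmetry row 4 alone has about half of the 20% at 40% yield, so on that reading the one-product situations total about 11% + 10% = 21%.

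**6. Return of skipped kits.** No row or sentence provides for it. This matters when the leading arm is itself below 10: 9 v 3 has e = 6 and meets row 1, yet active cannot then reach 10 unless its kits come back. About 4% of triggered runs at 40% yield are of this kind.

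**The case against.** The strongest defence is proportionality. The study is descriptive, with no hypothesis tests and a sample size not set on statistical grounds, so no error rate is at risk. Filling a short arm is a declared operational aim. The table is only a guide, the assessment can be repeated, and the contingency is uncommon. In about 22% of triggered runs at 40% yield the shorter arm already has 10 subjects, so no further enrolment is needed to reach the target. The primary endpoint also requires a negative laboratory culture, which limits what subjective scoring alone can do. All of this stands, and it makes the point a modest one. It does not answer it: a descriptive percentage can still be distorted by enrolment time and site mix, the repeat is optional, and no reinstatement rule is written.

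Three stronger readings are tempting but not supported:
- **The objective loses its control.** It does not. At 13 v 7, all 20 subjects were randomised concurrently under mask. Only later additions lack a comparator.
- **Sites become unmasked.** No text breaks the mask. Bottles remain identical, only an unblinded statistician sees the counts, and the documents do not say how sites are told to skip kits. A site might infer from the skipped numbers that one product remains, but gaps also arise because the 7-day kits leave at the same time.
- **The SAP exceeds the protocol.** Section 9.2 read alone speaks of a ratio, but section 10.5.5 speaks of allocation more generally and delegates the details to the SAP.

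**Conclusion.** The point holds for subjects enrolled after row 1 or row 5 is applied and until any repeat assessment restores the other product. They are allocated deterministically, have no concurrent randomised 14-day comparator, and are pooled by arm with earlier subjects. This weakens the active-versus-vehicle contrast without removing it.

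The chance is about 5% to 11% over MITT yields of 60% to 40%, resting on assumed yields and independent binomial counts at the SAP's trigger. When it happens, a typical effect is that about 3 of the shorter arm's 10 target subjects are non-concurrent. That figure takes the goal to be the stated minimum of about 10 per arm, not parity between arms. The row 4 wording is a separate internal contradiction that must be reconciled whatever is decided on the rest. Overall this is a cheap improvement to the plan.

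**What to change.** 1. **Supportive table.** Add an MITT table of therapeutic cure for 14-day active versus 14-day vehicle, limited to subjects randomised before any kit-skipping. Cost: one extra table. Its limit is size: it holds only the subjects in place at the change, for example 13 v 7.
2. **Reconcile row 4**, so that the skipped product and the numbers from which the retained kit is drawn agree.
3. **Keep both 14-day products in the schedule.** In rows 1 and 5, and in rows 2 and 4 once row 4 is corrected, retain some randomly chosen leading-arm kits. Each block of six holds two kits of each 14-day product; keeping one leading-arm kit per block gives 2:1 toward the shorter arm.
4. **State when skipped kits return**, for example at a repeat assessment that meets row 3.

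Items 2 to 4 need SAP and kit-list wording. The downside of item 3 is a slower fill. To gain 3 MITT subjects at 40% yield, all-to-one allocation takes 3/0.40 = 7.5, about 8 subjects. At 2:1 it takes 7.5 x 3/2 = 11.25, about 11. At that yield the planned 75 are on average already used at the trigger (3 x 25 = 75), so the extra subjects come on top of plan, as Protocol 4.4 permits. If that is unacceptable, item 1 alone is still worth doing.

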6.1.7. Multicenter Studies

Not applicable to this study.

6.1.8. Multiple Comparisons/Multiplicity

No adjustments for multiple comparisons or multiplicity will be made.

6.1.9. Use of an Efficacy Subset of Subjects

Subjects with a clinical diagnosis of otomycosis confirmed by a positive fungal culture, who are randomized to study drug, have received at least one dose of study medication, and who do not have major protocol deviations will form the Per Protocol (PP) Population. The major protocol deviations will be defined at the time of evaluability evaluation, the time between the database soft lock and hard lock before unblinding.

Excluding subjects who have major protocol deviations will decrease the variability in treatment response and will allow for a better determination of dose-response relationship of miconazole.

